### **6.3 Data or safety monitoring committee**

The Steering committee will evaluate SAE every 6 months or upon request and report to the Global Drug Safety Physician.

## **7. STUDY MANAGEMENT**

### **7.1 Monitoring**

Before the study begins, a representative of AstraZeneca will visit the investigational site to

- determine the adequacy of the facilities

- discuss with the investigator(s) (and other personnel involved with the study) their responsibilities with regard to protocol adherence, and the responsibilities of AstraZeneca or its representatives.

During the study, a monitor from AstraZeneca or company representing AstraZeneca will have regular contacts with the investigational site, including visits to

- provide information and support to the investigator(s)
- confirm that facilities remain acceptable
- confirm that the investigational team is adhering to the protocol, that data are being accurately recorded in the case report forms (CRFs), and that investigational product accountability checks are being performed
- perform source data verification (a comparison of the data in the CRFs with the subject's records at the hospital or practice, and other records relevant to the study). This will require direct access to all original records for each subject (e.g., clinic charts).

The monitor or another AstraZeneca representative will be available between visits if the investigator(s) or other staff at the centre need information and advice.

## **7.2 Audits and inspections**

Authorized representatives of AstraZeneca, a regulatory authority, an Independent Ethics Committee (IEC) or an Institutional Review Board (IRB) may visit the centre to perform audits or inspections, including source data verification. The purpose of an AstraZeneca audit or inspection is to systematically and independently examine all study related activities and documents to determine whether these activities were conducted, and data were recorded, analysed, and accurately reported according to the protocol, Good Clinical Practice (GCP), guidelines of the International Conference on Harmonisation (ICH), and any applicable regulatory requirements. The investigator should contact AstraZeneca immediately if contacted by a regulatory agency about an inspection at his or her centre.

## **7.3 Training of staff**

The principal investigator will maintain a record of all individuals involved in the study (medical, nursing and other staff). He or she will ensure that appropriate training relevant to the study is given to all of these staff, and that any new information of relevance to the performance of this study is forwarded to the staff involved. Histopathological training will be held at investigators meetings.

## **7.4 Changes to the protocol**

Study procedures will not be changed without the mutual agreement of the international principal investigator(s) and AstraZeneca.

If it is necessary for the study protocol to be amended, the amendment or a new version of the study protocol must be notified to or approved by each IEC or IRB, and in many countries also the local regulatory authority, before implementation. Local requirements must be followed.

If a protocol amendment requires a change to a particular centre's Written Informed Consent Form, then AstraZeneca and the centre's IEC or IRB must be notified. Approval of the revised Written Informed Consent Form by AstraZeneca and by the IEC or IRB is required before the revised form is used.

AstraZeneca will distribute amendments and new versions of the protocol to each principal investigator(s), who in turn is responsible for the distribution of these documents to his or her IEC or IRB, and to the staff at his or her centre. The distribution of these documents to the regulatory authority will be handled according to local practice.

## **7.5 Study agreements**

The principal investigator at each centre must comply with all the terms, conditions, and obligations of the study agreement for this study. In the event of any inconsistency between this protocol and the study agreement, this study agreement shall prevail.

## **7.6 Genetic sampling and storage**

### **7.6.1 Collection of samples for genetic research**

Subjects will provide a blood sample as per visit schedule.

A single venous blood sample (approximately 10 mL) will be collected into a polypropylene tube containing ethylenediamine tetra-acetic acid (EDTA) and gently inverted a minimum of 5 times to mix thoroughly. Tubes will be labelled with the protocol study number, centre number, enrolment code and/or randomisation number and date of sample collection. No personal identifiers (subject name, initials or date of birth) will be placed on the tube or accompanying documentation. A record of the date of the subject consent to the genetic research and the date of the blood sample collection will be recorded in the appropriate Section of the CRF.

### **7.6.2 Sample processing and shipping**

Samples will be frozen (-20°C or below) and transported to the relevant DNA extraction laboratory within one month of collection and must remain frozen at all times.

Where possible samples should be shipped in batches and shipment should be coordinated with the receiving site to ensure that samples arrive within working hours. A requisition sheet, detailing the protocol study number, centre number, enrolment code and/or randomisation code and date of sample collection, should accompany the shipment

### **7.6.3 Storage and coding of DNA samples**

The processes adopted for the coding and storage of samples for genetic analysis are important to maintain subject confidentiality.

For all samples irrespective of the type of coding used the DNA will be extracted from the blood sample. The DNA sample will be assigned a unique number replacing the information on the sample tube. Thereafter, the DNA sample will be identifiable by the unique DNA number only. The DNA number will be used to identify the sample and corresponding data at the AstraZeneca genetics laboratories, or at the designated contract laboratory. No personal details identifying the individual will be available to any AstraZeneca employee working with the DNA.

The blood samples and data for genetic analysis in this study will be coded. Each blood sample will be labelled with the study number and subject number. Only the investigator will be able to link the blood sample to the individual subject. The sample and data will not be labelled with a personal identifier. The link between the subject enrolment/randomisation code and the DNA number will be maintained.

This link file and any corresponding genetic data will be stored in a secure environment, with restricted access within the Clinical Genotyping Group Laboratory Information Management System (LIMS) at . The link will be used to identify the relevant DNA samples for analysis, facilitate correlation of genotypic results with clinical data, allow regulatory audit and to trace samples for destruction in the case of withdrawal of consent. Access to the link file will require written authorisation from the Project Team Leader.

### **7.6.4 Summary of genetic assessments and analysis**

The purpose of the genetic research is to generate data for use in future retrospective analyses. Future analyses will explore genetic factors that may influence the disposition, efficacy, safety and tolerability to esomeprazole and/or susceptibility to or prognosis of gastroesophageal reflux disease (GERD) under investigation in this protocol. The results of the genetic research will not form part of the clinical study report for this study. The results may be pooled with genetic data from other studies on esomeprazole to generate hypotheses to be tested in future studies.

## **7.7 Volume of blood sampling and handling of biological samples**

The total volume of blood that will be drawn from each subject in this study is as follows (Table 6):

**Table 6 Volume of blood to be drawn from each subject**

Assessment		Sample volume (ml)	N of samples	Total volume (ml)
Safety	Clinical chemistry	Approx. 28.5	Approx. 6	Approx. 171
	Haematology	Approx. 4.5	Approx. 6	Approx. 27
Genotyping (optional)		Approx 10	1	Approx. 10
Total				Approx. 208

## 7.8 Study timetable and termination

First subject in (FSI) Q4 2001

Last subject in (LSI) Q4 2002

Last subject out (LSO) Q3 2013

### Planned duration of the study

End of study is defined as date of final database lock, which is the time point after which no patient will be exposed to study related activities. The study prolongation is expected to start in Q1 2007, and to be completed in Q4 2013

## 8. ETHICS

### 8.1 Ethics review

The final study protocol, including the final version of the Written Informed Consent Form, must be approved or given a favourable opinion in writing by an IEC or IRB as appropriate. The investigator must submit written approval to AstraZeneca before he or she can enrol any subject into the study.

The principal investigator(s) is responsible for informing the IEC or IRB of any amendment to the protocol in accordance with local requirements. In addition, the IEC or IRB must approve all advertising used to recruit subjects for the study. The IEC or IRB must reapprove the protocol annually, as local regulations require.

Either the investigator(s) or AstraZeneca must submit progress reports to the IEC or IRB according to local regulations and guidelines. The principal investigator(s) must also provide

the IEC or IRB with any reports of serious adverse events from the study site as local regulations require.

Where there is a genetic research, approval must be obtained for this genetic research and the associated genetic informed consent from the Ethics Committee. It must be clearly stated in the approval that this genetic research is approved. The investigator must submit written approval to AstraZeneca before any subject participates in this genetic research.

## **8.2 Ethical conduct of the study**

The study will be performed in accordance with the ethical principles in the Declaration of Helsinki (see Appendix C), Good Clinical Practice, and applicable regulatory requirements.

Subjects included into this study have a chronically troublesome disease in need of therapy. They are considered suitable for anti-reflux surgery and for long-term treatment with PPI. Even if the subject had not been included in this study, one of these two treatment options would have been chosen. Anti-reflux surgery is associated with post-operative morbidity during the convalescent period as well as a risk of post-operative complications. By including a subject into this study the investigator confirms that this has been taken into account and that according to his judgement the benefits the subject receives from the operation outweighs this risk.

The additional risk the subject is exposed to by participating in the study is associated with some assessments not included in routine clinical practise (4 extra endoscopies with biopsies). Biopsy taking is generally associated with minimal bleeding and only causes bleeding of clinical importance in extremely rare cases. Benefits of participating are long-term follow-up by a clinical specialist with special interest in GERD subjects, including additional assessments of symptoms and objective findings at specified intervals, as well as the opportunity to contact the doctor when needed throughout the study period.

## **8.3 Subject information and consent**

The principal investigator(s) at each centre will ensure that the subject is given full and adequate oral and written information about the nature, purpose, possible risk and benefit of the study. Subjects must also be notified that they are free to discontinue from the study at any time. The subject should be given the opportunity to ask questions and allowed time to consider the information provided.

The subject's signed and dated informed consent must be obtained before conducting any procedure specifically for the study and the prolongation, including the following:

- Collection of blood samples
- Collection of urine samples
- Physical examination

- Endoscopic examinations with biopsy sampling
- 24 hr ambulatory pH metry, manometry and SAP
- Completion of rating scales and questionnaires
- Withholding medical treatment for 2 weeks during run-in phase
- Intake of investigational product (5-year prolongation)

The principal investigator(s) must store the original, signed Written Informed Consent Form. A copy of the signed Written Informed Consent Form must be given to the subject.

A sample Written Informed Consent Form is enclosed (Appendix B). If modifications are made according to local requirements, the new version has to be approved by AstraZeneca.

The genetic research is optional and the subject may participate in the main study without participating in the genetic component. To participate in the genetic component of the study the subject must sign and date both the consent form for the main study (non-genetic components of the study) and the genetic component of the study. Copies of both signed and dated consent forms must be given to the subject and the original filed at the study centre. The principal investigator(s) is responsible for ensuring that consent is given freely and that the subject understands that they may freely discontinue the genetic aspect of the study at any time.

If modifications are made in the informed consent (non-genetic component) and/or informed consent (genetic component) according to local requirements, the new version has to be approved by AstraZeneca.

## **8.4 Subject data protection**

The Written Informed Consent Form will explain that study data will be stored in a computer database, maintaining confidentiality in accordance with national data legislation. Subjects in this database will be identified by initials or subject number only. The Written Informed Consent Form will also explain that for data verification purposes, authorized representatives of AstraZeneca, a regulatory authority, an IEC or IRB may require direct access to parts of the hospital or practice records relevant to the study, including subjects' medical history.

## **9. EMERGENCY PROCEDURES**

### **9.1 AstraZeneca emergency contact procedure**

Due to the nature of the population participating in this study (GERD subjects) no immediate emergency concerns related to the disease, drug or the assessments can be foreseen. Any

emergency situation should be managed and handled by the participating clinics after their local emergency protocols.

## **9.2 Procedures in case of medical emergency**

The principal investigator(s) is responsible for ensuring that procedures and expertise are available to cope with medical emergencies during the study.

## **9.3 Procedures in case of overdose**

There is no experience to date with deliberate overdose. Data are limited but single doses of 80 mg esomeprazole were uneventful. No specific antidote is known. Esomeprazole is extensively protein bound and is therefore not readily dialyzable. As in any case of overdose, treatment should be symptomatic and general supportive measures should be utilised.

## **9.4 Procedures in case of pregnancy**

Since esomeprazole is a new drug, there is no/limited information on its effects in humans on the unborn baby. Data available from animal studies to date do not indicate direct or indirect harmful effects with respect to pregnancy, embryonal/fetal development, parturition or postnatal development.

Consequently, women must be either post-menopausal, permanently surgically sterilized or, if of childbearing potential, using a reliable form of contraception prior to and during participation in the study. A subject who during the trial intends to or actually becomes pregnant should contact the investigator. The investigator must notify AstraZeneca and withdraw the subject from the study. Pregnancy itself is not regarded as an adverse event unless there is a suspicion that the investigational product under study may have interfered with the effectiveness of a contraceptive medication. However, the outcome of all pregnancies (spontaneous miscarriage, elective termination, normal birth or congenital abnormality) must be followed up and documented even if the subject was discontinued from the study.

All reports of congenital abnormalities/birth defects are SAEs. Spontaneous miscarriages should also be reported and handled as SAEs. Elective abortions without complications should not be handled as AEs. All outcomes of pregnancy must be reported to AstraZeneca on the pregnancy outcomes report form.

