### **3.3.5 Discontinuation of subjects from treatment or assessment**

#### **3.3.5.1 Criteria for discontinuation**

Subjects may be discontinued from study treatment and assessments at any time, at the discretion of the investigator(s). A subject may, however, continue the study under exceptional circumstances (e.g. if continuation of study treatment or follow-up actions are necessary for the subjects safety and well-being, and the continuation of the study is not expected to be associated with any risk or discomfort for the subject). Specific reasons for discontinuing a subject from this study are:

1. Withdrawal of informed consent
2. Unwillingness to continue the study or lost to follow-up.
3. Any unacceptable adverse event, including laboratory result or physical findings, as judged by the investigator
4. Any “alarm symptoms” which, in the investigator’s judgement, requires treatment outside this protocol.
5. Continuous need for/intake of drugs listed under Section [3.3.4](#) criteria 7.
6. Protocol non-compliance as judged by the investigator
7. Classified as treatment failure
8. Pregnancy
9. Incorrect enrolment or randomization of subject
10. Other reason specified by the investigator.

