### **3.3.5.4 Procedures for discontinuation**

The subject should return for a clinic visit at the time of, or soon after discontinuation with maintained medication (medical arm) for the following assessments:

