#### **Discontinuation after randomization:**

- Endoscopy including biopsies and *Hp* status
- Laboratory screening
- Body weight
- All SAE and those AE causing premature discontinuation of study drug and/or study
- Patient reported outcomes
- Symptoms
- 24 hour pH metry and SAP
- The reason for discontinuation

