### **3.4.3 Method of assigning subjects to treatment groups**

Individual treatment codes, indicating the treatment allocation for each randomized subject, will be provided by AstraZeneca.

The subjects will be randomized into either esomeprazole or anti-reflux surgery.

Subject eligibility will be established before treatment randomization. Subjects will be randomized strictly sequentially. If a subject discontinues from the study, the randomization number will not be reused, and the subject will not be allowed to re-enter the study.

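### Section 3.3.5.4 recalls a subject withdrawn for pregnancy, still on esomeprazole if in the medical arm, for endoscopy with biopsies and pH metry, and neither it nor Section 9.4 makes an exception

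*Protocol*

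**What the plan says.** Section 9.4 opens with its reason for caution: "Since esomeprazole is a new drug, there is no/limited information on its effects in humans on the unborn baby". The next sentence adds that animal studies to date show no harmful effect. The section then asks for contraception and sets the procedure: "A subject who during the trial intends to or actually becomes pregnant should contact the investigator", and "The investigator must notify AstraZeneca and withdraw the subject from the study". It requires follow-up and reporting of the pregnancy outcome. It does not say when esomeprazole is to stop, and it does not mention the discontinuation visit.

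Section 3.3.5.1 introduces a numbered list with "Specific reasons for discontinuing a subject from this study are". Pregnancy is item 8.

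Section 3.3.5.4 sets out what happens next: "The subject should return for a clinic visit at the time of, or soon after discontinuation with maintained medication (medical arm". For discontinuation after randomization it lists eight items, among them "Endoscopy including biopsies" and "24 hour pH metry and SAP". The discontinuation columns of Tables 1 and 2 mark the same tests. Their footnotes (17 in Table 1, h in Table 2) refer to premature discontinuation without distinguishing the reason. The list for the 10-year study period in Section 3.1 also calls for endoscopy at early discontinuation.

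**The concern.** The two procedures pull against each other. Section 9.4 removes a pregnant woman from the study as a precaution about the drug. Section 3.3.5.4 applies to her because she has been removed, and it contemplates that she stays on the drug until a clinic visit and then has an endoscopy with biopsies and a 24-hour pH recording.

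At stake is the safety of individual women. A site that follows the checklist literally could prolong exposure to esomeprazole in early pregnancy and carry out invasive tests whose only trigger is the pregnancy. The case is foreseeable: Section 3.3.2 admits women from age 18, Section 3.3.4 accepts those using contraception, and follow-up lasts ten years.

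**Working it through.** The protocol gives no figure for this point, so the check is a reading of the sections together.

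1. **Does the discontinuation visit apply to pregnancy?** Pregnancy is item 8 of 3.3.5.1. The post-randomization list in 3.3.5.4 is not limited to particular items of 3.3.5.1, and neither table footnote limits it. So it applies.

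2. **Does anything stop the drug first?** Section 9.4 speaks of withdrawal from the study and is silent on tablets. Section 3.3.5.4 has the medical arm attend while still medicated. Read together, the only instruction about drug between report and visit is to continue it. The interval is not given in days, and it is zero if the visit takes place at discontinuation.

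3. **Who is exposed to what?** Continued drug concerns the medical arm. Endoscopy and pH metry concern both arms.

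4. **How much of the visit is affected?** The eight items are endoscopy with biopsies and Hp status, laboratory screen, body weight, adverse events, patient-reported outcomes, symptoms, pH metry with SAP, and the reason for discontinuation. Two are invasive instrumental tests, so 8 − 2 = 6 can stay.

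5. **Does the primary analysis need the two tests?** No. Treatment failure (Section 4.1) rests on two questions about symptom control and drug need, plus surgical events. Section 6.2.3 censors discontinuations for reasons other than failure. Endoscopy and pH results are summarized descriptively.

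6. **Would pregnancy withdrawals matter for precision?** This bears only on a wider reading taken up in the verdict. Section 6.1 plans for at most 8 percentage points with 275 per arm and 70% success. The half-width is 1.96 × √(0.7 × 0.3 × (1/n₁ + 1/n₂)).
   - 275 per arm: 7.66 points, which agrees with the plan.
   - 272 per arm (3 wholly lost in each): 7.70 points.
   - 264 per arm (11 wholly lost in each): 7.82 points.

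   The losses of 3 to 11 are assumptions, since the protocol gives no pregnancy rate.

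**The case against.** The other side has several fair points.

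- Section 3.3.5.4 uses the language of recommendation, and the visit may fall on the day of discontinuation, in which case no drug day is added. Both are true and limit the exposure. But Section 3.1 states endoscopy at early discontinuation as something that will be done, and a same-day visit still includes the tests.
- Section 9.4 is the specific section and lists its own steps, so it could be said to displace the general checklist. It does not say so, and the checklist contains no carve-out that points to 9.4.
- Section 3.3.5.1 describes discontinuation as covering treatment as well as assessments, so withdrawal might already mean stopping tablets. That would be a natural reading if 3.3.5.4 did not provide for continued medication up to the visit.
- The stated reason is limited information, not known harm, and Section 8.2 describes clinically important bleeding from biopsies as extremely rare. This lowers the likely harm. Section 8.2 does not discuss pregnancy, however, and Section 3.3.4 excludes pregnancy at entry, so the protocol is cautious elsewhere.
- Section 3.3.5.2 asks for assessment only where possible. That section deals with voluntary discontinuation, and withdrawal under 9.4 is required.
- Appendix F (additional safety information) was not available. If it contains a pregnancy exception, the gap is one of cross-reference.

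These points reduce the force of the concern. The missing exception remains.

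**Conclusion.** The point holds as a gap in patient-safety wording, of low severity. As written, the protocol does not exempt a pregnant woman from continued esomeprazole before, or invasive tests at, a visit that she needs only because she is pregnant. This is at odds with the protocol's own precaution. The number of women and the days of extra exposure cannot be derived from the document. There is no effect on the primary comparison. The conclusion assumes that no exception stands in the appendices not shown.

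A reader might go further and infer that withdrawing pregnant women from the study is itself a flaw, because the reason given concerns only the drug and Section 3.4.3 makes withdrawal final: "the randomization number will not be reused, and the subject will not be allowed to re-enter the study". The documents do not support calling that an error. Withdrawal, no re-entry and censoring are consistent across 9.4, 3.3.5.1, 3.4.3 and 6.2.3. The rule is the same in both arms, so no bias between them is shown. Under the assumed losses, precision stays within the planned 8 points.

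For one woman withdrawn just after visit 8, the loss is 13 visits with symptom assessment (8 at visits 9 to 16, and 5 at visits 31, 33, 35, 37 and 39), partly offset by the 5- and 10-year telephone calls. That is lost descriptive follow-up. Keeping such women in the study would need rules for resuming drug, lactation, intended pregnancy and failure while off drug. It is a design preference, and no change to it is proposed here.

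Nor does the protocol show that the tests or the drug would cause harm; the point is that the text does not apply its own caution.

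**What to change.** - **Section 9.4:** add a sentence that esomeprazole stops as soon as pregnancy is reported. Worded without reference to arm, it also covers a surgical-arm woman who is taking the drug while awaiting surgery or under Section 3.4.5.
- **Section 3.3.5.4, and footnotes 17 (Table 1) and h (Table 2):** exempt pregnancy from continued medication, endoscopy with biopsies and pH metry. Keep symptoms, questionnaires, adverse events, body weight, laboratory screen and the reason for discontinuation. The early-discontinuation endoscopy in Section 3.1 needs the same exception.

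No change to the analysis is required.

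The cost is the loss of one endoscopy (with histology and Hp status) and one pH recording at discontinuation for each such woman, plus a short amendment. Under Section 7.4 the amendment must be notified to or approved by each ethics committee, and in many of the 11 countries also by the regulatory authority. If the consent form has to change, that needs approval too; its text was not available. Adding these sentences to the next amendment would keep the extra work small.
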